12.6. Ancillary Objective #5

Estimate the incidence of ArcticLine Catheter-related and ArcticLine cryoablation procedure-related serious adverse events (SAE) through the 6 month visit.

Endpoint Definition

ArcticLine Catheter-related or ArcticLine cryoablation procedure-related SAEs, as adjudicated by the Clinical Events Committee (CEC).

Analysis Methods

Kaplan-Meier methods will be used to estimate event percentages separately for each of the events listed above. Time 0 will be the time of the index ablation and subjects without an event will be censored at their last documented time in the study (e.g., follow-up, exit, death). Though Kaplan-Meier methods will be used, only point estimates for the rates at 6 months (not graphs) will be reported.

Note: Safety data collected beyond the six month visit due to CIP Version 4 follow-up requirements will be adjudicated and included in the final report.

Determination of Patients for Analysis

All subjects undergoing an ArcticLine cryoablation procedure will be included. An ArcticLine cryoablation procedure is considered to have occurred once the ArcticLine Catheter is introduced into the vasculature.

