4.27 Ancillary Objective #7

Estimate the incidence of adverse events (AEs) through the 6 month visit.

Ancillary Endpoint #7

Characterize adverse events through the 6 month visit, described as follows:

[figure not shown]
- Atrioesophageal fistula
- Cardiac perforation/tamponade
- Cerebrovascular accident
- Coronary artery spasm
- Death
- Esophageal injury
- Lung injury (including hemoptysis)
- Major bleeding
- Myocardial infarction
- Pericarditis
- Phrenic nerve injury (ongoing from hospital discharge)
- Pulmonary vein stenosis

- Symptomatic persistent iatrogenic atrial septal defect
- Transient ischemic attack
- Vagal nerve injury
- Vascular access complications

5. Investigation Plan

The purpose of the study is to collect preliminary safety and effectiveness data on the ArcticLine Catheter when used to treat persistent AF and right atrial CTI dependent AFL, or “typical atrial flutter”. These data will be used to guide subsequent product development activities for the ArcticLine Catheter, including feedback on device design and input into a future pivotal study.

Medtronic is sponsoring the ArcticLine Feasibility Study: a prospective, interventional, multicenter, non-randomized, single arm, unblinded clinical study. The study design diagram is shown in Figure 1. Up to 15 subjects will be enrolled in up to 4 centers in the United States and Canada, and will be treated with the ArcticLine Catheter.

6. Determination of Sample Size

The expected sample size is approximately 15 subjects, and is based on historical precedent for other feasibility studies, rather than a statistical derivation. The sample size of 15 treated subjects for this study was chosen with the goal to collect preliminary safety and effectiveness data on the ArcticLine

Catheter's use in both the left and right atrium. Assuming there are 15 ArcticLine cryoablation procedures in the study and the ArcticLine cryoablation procedure-related SAE rate is 6.7% (1/15 subjects: the rate of cryoablation procedure events in the STOP AF pivotal trial [PMA #P100010] was 3.1%), the exact 95% confidence interval will have a width of 32%.

7. Statistical Methods

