7.2.2 Primary Objective

Estimate the incidence of ArcticLine Catheter-related and ArcticLine cryoablation procedure related Serious Adverse Events (SAEs) with an onset date within 7 days post-procedure.

Endpoint Definition

ArcticLine Catheter-related or ArcticLine cryoablation procedure-related SAEs, with an onset date within 7 days post-procedure (except as noted below), as adjudicated by the Clinical Events Committee (CEC), described as follows:

- Atrioesophageal fistula*

* Includes atrioesophageal fistula with an onset date at any time after the study cryoablation procedure and is adjudicated by the CEC as either ArcticLine Catheter related or ArcticLine cryoablation procedure-related.

- Cardiac perforation/tamponade
- Cerebrovascular accident
- Death
- Esophageal injury
- Major bleeding
- Myocardial infarction
- Pericarditis
- Phrenic nerve injury (ongoing at hospital discharge)
- Transient ischemic attack
- Vagal nerve injury resulting in esophageal dysmotility or gastroparesis
- Vascular access complications

The percentage of catheter related and cryoablation procedure related SAEs will be calculated as the number of procedures with at least one SAE meeting the endpoint definition divided by the number of cryoablation procedures. Exact methods will be used to construct a 95% confidence interval for the percentage of procedures with an SAE.

Each procedure will count towards the primary endpoint, so subjects with repeat ArcticLine ablations will contribute more than once to the denominator.

Sensitivity Analysis: Independence of Primary Events

Note: With version 3 of this SAP, all procedures are complete. No repeat ablations have been or will be performed, so this sensitivity analysis will not be performed.

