ArcticLine Catheter-related or ArcticLine cryoablation procedure-related SAEs, as adjudicated by the Clinical Events Committee (CEC).

Analysis Methods

The number of SAEs, the number of subjects with SAEs, and the percent of subjects with SAEs will be provided in tabular form. Listings will be provided for any data collected relevant to this objective that occurred after 6 months, due to CIP v5 follow-up requirements.

Determination of Subjects for Analysis

All ArcticLine treated subjects will be included.

7.28 Ancillary Objective 6

Characterize procedural data:

- Total procedure time
- Total ArcticLine Catheter use time
- Left atrial dwell time

- Total fluoroscopy time
- Total fluoroscopy time during ArcticLine Catheter use
- Application duration
- Number of applications
- Fluoroscopy dose

Ancillary Endpoint #6

- Total procedure time is defined as time from first venous access to time of last catheter removal.

What was the time of first venous access FVACCTM_PRSTDTC HH:MM (24 hour clock)

What was the time of last sheath removal LSHTRTM_PRSTDTC HH:MM (24 hour clock)

- Total ArcticLine Catheter use time is defined as cumulative time from introduction of ArcticLine Catheter into the body to its removal.

What was the time of ArcticLine catheter insertion ALCPTM_PRSTDTC HH:MM (24 hour clock)

What was the time of ArcticLine catheter removal ALCTRTM_PRSTDTC HH:MM (24 hour clock)

- Left atrial dwell time is defined as time from transseptal puncture to time of removal of last sheath/catheter from the left atrium.

What was the time of transseptal puncture TRNSPTM_PRSTDTC HH:MM (24 hour clock)

What was the time of last sheath removal LSHTRTM_PRSTDTC HH:MM (24 hour clock)

- Total fluoroscopy time is defined as total fluoroscopy time used during the procedure.

What was the fluoroscopy timer at time of first ablation catheter insertion FFABLTM_PRSTDTC HH:MM:SS

What was the fluoroscopy timer at the end of procedure FPRENTM_PRSTDTC HH:MM:SS

- Total fluoroscopy time during ArcticLine Catheter use is defined as the cumulative fluoroscopy time from each introduction of ArcticLine Catheter into the body to its removal.

What was the fluoroscopy timer at time of ArcticLine catheter insertion FACLITM_PRSTDTC HH:MM:SS

What was the fluoroscopy timer at time of ArcticLine catheter removal FACLRTM_PRSTDTC HH:MM:SS

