Calculation of application duration and number of applications will be calculated from data in the Non-PVI Energy Application CRF where the Catheter number is equal to the row from the subject’s Device Identification CRF where the model number is “ArcticLine Catheter (2AL35)”. Rows from other catheters (non-Medtronic RF catheters, Freezor MAX) will not be included in these calculations. In the study’s final report (which is the primary concern of this SAP), application duration and number of applications will be calculated using all freezes, regardless of duration. However, it is noted that in publications, these metrics may be defined slightly differently: only ArcticLine applications ≥ 60 seconds in duration may be included in summary statistics, while the rest will be considered as “aborted freezes”.

Determination of Subjects for Analysis

All ArcticLine treated subjects will be included.

7.29 Ancillary Objective 7

Estimate the incidence of adverse events (AEs) through the 6 month visit.

Ancillary Endpoint #7

Characterize adverse events through the 6 month visit, described as follows:

- Atrioesophageal fistula
- Cardiac perforation/tamponade
- Cerebrovascular accident
- Coronary artery spasm
- Death
- Esophageal injury
- Lung injury (including hemoptysis)
- Major bleeding
- Myocardial infarction
- Pericarditis
- Phrenic nerve injury (ongoing from hospital discharge)
- Pulmonary vein stenosis
- Symptomatic persistent iatrogenic atrial septal defect
- Transient ischemic attack
- Vagal nerve injury
- Vascular access complications

Analysis Methods

The number of AEs, the number of subjects with AEs, and the percent of subjects with AEs will be provided in tabular form. The results of this endpoint may be combined with ancillary endpoint #5 with a column for AEs and a column for SAEs. Listings will be provided for any data collected relevant to this objective that occurred after 6 months, due to CIP v4 follow-up requirements.

Determination of Subjects for Analysis

All ArcticLine treated subjects will be included.

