7.8 Changes to Planned Analysis

Additional details on analysis methods outlined in version 5 of the ArcticLine CIP have been provided in this SAP. Version 3 of this document outlines four changes. First, updates have been made to reflect the new lower sample size of 15 treated subjects that is now expected. Second, the reduced study duration from 12 months to 6 months has been incorporated into the protocol and approved by the FDA and Health Canada. Third, Kapan-Meier analyses have been removed from Ancillary Objectives #5 and #7 because the smaller sample size and reduced duration (6 months vs 12 months) renders this analysis inappropriate. Finally, clarification for having only one planned interim analysis has been made.

Version 2 of the SAP outlined methods for analyzing the expected 20 subjects, which was the expectation at the time of that revision. Further, SAP v2 added clarification on handling “aborted freezes” (applications of ArcticLine < 60 seconds) in the calculation of metrics in Ancillary Objective #6.

Additionally, from version 1 of the SAP, there were three components to the analysis added to this SAP of which the analysis plan in the CIP makes no mention. First, in response to an FDA request, summaries of available data for ancillary objectives 1-3 (assessing acute success of the ArcticLine ablation procedure) will be included in the interim analysis submitted after N=15 subjects have received index cryoablations. Second, in response to Institutional Review Board (IRB) concerns, an analysis is described which investigates the robustness of assumptions involved in treating the primary endpoint as a binomial event. Finally, to better account for early exits and censored data, and to better utilize available information on time to recurrence, a Kaplan-Meier analysis for ancillary objective #4 (chronic treatment success) was outlined.

Analytical deviations from procedures in this SAP may be addressed by the release of newer SAP versions, or will be described in the final report, along with the rationale for the deviation.

8. Validation Requirements

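### Objectives 5 and 7 report 6-month safety incidence in 15 subjects as a bare percentage, with no confidence interval and no settled rule for event-free early exits

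*SAP*

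**What the plan says.** Protocol 12.6 (Objective 5) states that "Kaplan-Meier methods will be used to estimate event percentages separately". Time runs from the index ablation, and event-free subjects are censored when last documented in the study. Protocol 12.8 plans the same estimator for Objective 7. Both sections report only the 6-month point estimate, with no interval.

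The SAP replaces this. For Objective 5 (7.27) it gives the number of SAEs and of subjects affected, and "the percent of subjects with SAEs will be provided in tabular form". For Objective 7 (7.29), "the percent of subjects with AEs will be provided in tabular form". In both sections the analysis population is all ArcticLine treated subjects. SAP 7.8 declares the change, saying that the smaller sample and the shorter follow-up "renders this analysis inappropriate".

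The other objectives are treated differently:

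- **Primary objective (SAP 7.2.2):** "Exact methods will be used to construct a 95% confidence interval for the percentage of procedures with an SAE".
- **Objectives 1 to 3 (SAP 7.23 to 7.25):** exact Clopper-Pearson 95% intervals.
- **Objective 4 (SAP 7.26):** Kaplan-Meier at 6 months with a log-log 95% interval.

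SAP 7.4 rules out imputation and describes the primary and all ancillary analyses as complete-case, under the assumption that data are missing completely at random.

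**The concern.** Objectives 5 and 7 are the trial's broadest safety summaries. Objective 5 covers every CEC-adjudicated related SAE, whereas the primary endpoint is confined to a list of event types and, apart from atrioesophageal fistula, to 7 days. Both are framed as estimation, and the results are meant to inform a pivotal study. A bare 0% or 6.7% from 15 subjects says nothing about how large a risk the data leave open.

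The second issue is the denominator. Treated subjects who leave early are not replaced (Protocol 5.1). If such a subject stays in the denominator without an event, a few weeks of observation count as 6 event-free months, and any resulting error is toward apparent safety. If the subject is dropped as an incomplete case, the denominator shrinks. The SAP does not say which applies.

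**Working it through.** **Inputs.** n = 15 treated subjects (SAP section 6; Protocol 12.1). The documents give no early-exit rate, so 0 to 4 exits out of 15 is an assumed range.

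**Step 1: reproduce the plan's own figure.** SAP section 6 says "Assuming there are 15 ArcticLine cryoablation procedures in the study" and the "SAE rate is 6.7% (1/15 subjects"), then "the exact 95% confidence interval will have a width of 32" per cent. The Clopper-Pearson limits for 1/15 are:

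- Lower: solve 1 − (1 − p)^15 = 0.025, so p = 1 − 0.975^(1/15) = 0.17%.
- Upper: solve (1 − p)^15 + 15p(1 − p)^14 = 0.025, so p = 31.95%.

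The width is 31.8 percentage points, which rounds to the stated 32. A Wilson interval would be 28.6 points wide, so the SAP figure is Clopper-Pearson.

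**Step 2: apply the same method to Objectives 5 and 7.** For zero events the upper limit is 1 − 0.025^(1/15) = 21.8%.

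| Subjects with an event | Percent | Exact 95% interval |
|---|---|---|
| 0/15 | 0% | 0 to 21.8% |
| 1/15 | 6.7% | 0.2 to 31.9% |
| 2/15 | 13.3% | 1.7 to 40.5% |
| 3/15 | 20.0% | 4.3 to 48.1% |

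A true risk of 10% would still give 0/15 with probability 0.9^15 = 20.6%.

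**Step 3: early exits.** Suppose d subjects exit before any of e events occurs, which is the worst case. The crude figure is e/15. Kaplan-Meier is 1 − (15 − d − e)/(15 − d) = e/(15 − d). In this arrangement, dropping the exits as incomplete cases gives the same value.

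| Exits d | e = 1: crude | e = 1: Kaplan-Meier | e = 2: crude | e = 2: Kaplan-Meier |
|---|---|---|---|---|
| 0 | 6.7% | 6.7% | 13.3% | 13.3% |
| 1 | 6.7% | 7.1% | 13.3% | 14.3% |
| 2 | 6.7% | 7.7% | 13.3% | 15.4% |
| 3 | 6.7% | 8.3% | 13.3% | 16.7% |
| 4 | 6.7% | 9.1% | 13.3% | 18.2% |

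For one event the gap runs from 1/14 − 1/15 = 0.5 points to 1/11 − 1/15 = 2.4 points. For two events it runs from 2/14 − 2/15 = 1.0 point to 2/11 − 2/15 = 4.8 points. If the events come before the exits, Kaplan-Meier equals the crude figure. With no events every method gives 0%, but the denominator still moves the exact upper limit: 21.8% for 0/15 against 26.5% for 0/12.

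**Step 4: the denominator rules side by side.** SAP 7.27 and 7.29 include all treated subjects and state no follow-up requirement or censoring rule. SAP 7.4 says complete cases, but defines an incomplete case only for the primary endpoint. Protocol 8.12 says that data up to exit will be used, which fits poorly with dropping such subjects altogether. No passage settles how an event-free early exit is counted.

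**Step 5: the reason for removing Kaplan-Meier.** The current protocol, version 5, already has 15 subjects and 6 months, and it retains Kaplan-Meier in 12.6 and 12.8. The SAP states that it is based on that version. It also uses Kaplan-Meier for Objective 4 over the same 6 months, in at most the same 15 subjects. In 7.8 it explains that choice partly by the need to handle early exits and censoring, a need that Objectives 5 and 7 share.

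**The case against.** The strongest reply is that this is a feasibility study with no hypotheses and a sample size not derived statistically. The SAP already shows how wide an exact interval is at 1/15. Counts are tabulated, so a reader could work out the interval, and the Objective 7 endpoint is worded as characterization. This bears on severity, but it does not explain why these two estimates lack the interval that the primary objective and Objectives 1 to 3 receive.

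Three stronger readings are tempting, and the documents do not support them:

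- **That removing Kaplan-Meier removed the interval or created the 0/15 problem.** The protocol planned point estimates only, and Kaplan-Meier is also 0% when there are no events. Only an interval answers that concern.
- **That early exits are definitely counted as event-free.** This is an inference from the all-treated population, and the complete-case statement in SAP 7.4 points the other way. What is established is an unreconciled denominator.
- **That the SAP departs silently from the protocol.** SAP 7.8 names the change and gives a reason, and the protocol leaves further detail of methods to the SAP.

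Objective 4 is also not an exact parallel. Its Kaplan-Meier analysis is limited to subjects with confirmed acute block, and SAP 7.8 also cites the use of time-to-recurrence information. Its Holter percentage has no stated interval either. The Kaplan-Meier in Protocol 12.6 and 12.8 has limits of its own: it censors at death, which can overstate the incidence of non-fatal events, and 12.6 refers to a list of events that it does not contain. These points stand, and they argue against making Kaplan-Meier the main result.

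**Conclusion.** The concern holds as a modest, inexpensive improvement. The firm part is the missing interval, which rests only on n = 15 and on a method the SAP already uses.

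The denominator ambiguity is also real, but its numerical effect is conditional. It depends on an assumed 1 to 4 exits, all before the events, and even the largest gap (4.8 points) is small beside the exact interval for 2/15, which is about 39 points wide (40.5 − 1.7). It disappears with complete follow-up.

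The stated reason for dropping Kaplan-Meier is weak, but that supports only a sensitivity estimate. It does not show that the reported percentages will be materially biased.

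**What to change.** 1. In SAP 7.27 and 7.29, add an exact (Clopper-Pearson) 95% interval to each subject-level percentage. For Objective 7, which lists 16 event types, the interval depends only on the count and the denominator, so it needs no new method.
2. State how a treated subject who exits before the 6-month visit without an event is counted, make SAP 7.4 agree, and report the number followed to that visit beside each percentage.
3. If any treated subject exits early, add a 6-month Kaplan-Meier estimate with its own interval as a sensitivity result; the log-log form in SAP 7.26 would serve. Keep the exact interval attached to the crude percentage so that estimate and interval match. With no events the log-log interval cannot be computed, and the exact interval stands alone. For Objective 5, define the event for this estimate, for example the first related SAE.

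The cost is a few extra table columns and a sentence or two in the SAP. The intervals will look wide, which is an honest picture of 15 subjects.

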4.1.7. Ancillary Objective #6

Characterize procedural data:

- Total procedure time
- Total ArcticLine Catheter use time
- Left atrial dwell time
- Total fluoroscopy time
- Total fluoroscopy time during ArcticLine Catheter use
- Application duration
- Number of applications
- Fluoroscopy dose

Ancillary Endpoint #6

- Total procedure time is defined as time from first venous access to time of last catheter removal.
- Total ArcticLine Catheter use time is defined as cumulative time from each introduction of ArcticLine Catheter into the body to its removal.
- Left atrial dwell time is defined as time from transseptal puncture to time of removal of last sheath/catheter from the left atrium.
- Total fluoroscopy time is defined as total fluoroscopy time used during the procedure.
- Total fluoroscopy time during ArcticLine Catheter use is defined as the cumulative fluoroscopy time from each introduction of ArcticLine Catheter into the body to its removal.
- Application duration is defined as total duration in which cryoablation from the ArcticLine Catheter is applied to cardiac tissue overall and individually to each target area.
- Number of applications is defined as the total number of times in which the ArcticLine Catheter was used to ablate cardiac tissue overall and individually to each target area.
- Total fluoroscopy dose is defined as the amount of radiation deposited into the tissue, measured in Gy or mGy units.

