8.4. Procedure

The Investigator is to perform the procedure according to the procedural steps in this CIP and the applicable Instructions for Use for all devices (except for investigational uses as described in this CIP). Current recommendations for anticoagulation are found in the 2017 HRS/EHRA/ECAS/APHS/SOLAECE Expert Consensus Statement on Catheter and Surgical Ablation of Atrial Fibrillation² and 2014 Focused Update on the Canadian Cardiovascular Society Guidelines for the Management of Atrial Fibrillation.¹⁷

8.4.1. High Level Procedure Overview:

Appropriate sedation and venous access should be attained per the Investigator's standard practice according to their institution's pre-established procedures/guidelines at the time of the procedure. Investigator may choose compatible guidewires and mapping catheters at their discretion. The FlexCath Advance 12Fr sheath must be used for the deployment of the Arctic Front Advance and ArcticLine ablation catheters. Deploy diagnostic catheters and perform transseptal puncture.

Perform a baseline voltage map of the left atrium using a 3D mapping system (e.g. NavX, Rhythmia). Recommended settings for minimum voltage in this study is 0.2mV.

Perform baseline mapping of the pulmonary veins to assess for pulmonary vein potentials using a circular mapping catheter (e.g. Achieve Advance) to determine if PVI is required. If yes, perform the pulmonary vein isolation procedure using Arctic Front Advance Catheter as per Section 8.4.5.

If PVI ablation is performed, repeat voltage mapping of the left atrium using a 3D mapping system.

If the investigator determines the subject should move forward with ArcticLine ablation, perform the following required linear ablations using the ArcticLine Catheter as per Section 8.4.6:

- Left atrial roof line
- Left atrial posterior wall line

Note: An example where the investigator may choose not to move forward with ArcticLine ablation and instead, exit the subject from the study, is when a subject has previously undergone PVI and has minimal pulmonary vein reconnection which, in the opinion of the investigator, only requires touch-up ablation.

¹⁷ Verma A, et al. 2014 Focused Update of the Canadian Cardiovascular Society Guidelines for the Management of Atrial Fibrillation. *Canadian Journal of Cardiology*. 30 (2014) 1114-1130.

At the investigator's discretion, perform optional linear ablations at the following anatomic targets using the ArcticLine Catheter:

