12.7. Ancillary Objective #6

Characterize procedural data:

- Total procedure time
- Total ArcticLine Catheter use time
- Left atrial dwell time
- Total fluoroscopy time
- Total fluoroscopy time during ArcticLine Catheter use
- Application duration
- Number of applications
- Fluoroscopy dose

Endpoint Definition

- Total procedure time is defined as time from first venous access to time of last catheter removal.
- Total ArcticLine Catheter use time is defined as cumulative time from each introduction of ArcticLine Catheter into the body to its removal.
- Left atrial dwell time is defined as time from transseptal puncture to time of removal of last sheath/catheter from the left atrium.
- Total fluoroscopy time is defined as total fluoroscopy time used during the procedure.
- Total fluoroscopy time during ArcticLine Catheter use is defined as the cumulative fluoroscopy time from each introduction of ArcticLine Catheter into the body to its removal.
- Application duration is defined as total duration in which cryoablation from the ArcticLine Catheter is applied to cardiac tissue overall and individually to each target area.
- Number of applications is defined as the total number of times in which the ArcticLine Catheter was used to ablate cardiac tissue overall and individually to each target area.
- Total fluoroscopy dose is defined as the amount of radiation deposited into the tissue, measured in Gy or mGy units.

Analysis Methods

Standard statistics (e.g., mean, standard deviation) will be used to summarize each variable. Data from index cryoablations and repeat cryoablations will be reported separately.

Determination of Patients for Analysis

All subjects undergoing a cryoablation procedure will be included. A cryoablation procedure is considered to have occurred once the skin is punctured.

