- Application duration is defined as total duration in which cryoablation from the ArcticLine Catheter is applied to cardiac tissue overall and individually to each target area.

- Number of applications is defined as the total number of times in which the ArcticLine Catheter was used to ablate cardiac tissue overall and individually to each target area.
- Total fluoroscopy dose is defined as the amount of radiation deposited into the tissue, measured in Gy or mGy units.

Analysis Methods

The five time metrics (total procedure time, ArcticLine catheter use time, left atrial dwell time, total fluoroscopy time and total fluoroscopy time during ArcticLine use) are calculated as the difference between a single start time and a single end time, as captured in the “Procedure Times” section of the PROCEDURE CRF. At the time of this SAP, the CRF does not allow for the capture of timing for multiple ArcticLine catheter insertions and removals. If multiple ArcticLine insertions and removals occur in an ablation, sites should be instructed to record the first insertion and last removal, and the metric will be calculated from the two CRF fields described above.

Non PVI Ablation Energy Application

Application Sequence Number	Catheter Number	Location	Phrenic Nerve Monitoring Performed	Coldest Temperature (C)	Ablation Start Time	Duration of Ablation (seconds)
1		APCATLC_PRLOC / ABLATION LOCATION / 1	 CMAP  PACING OF RIGHT PHRENIC NERVE  PACING OF LEFT PHRENIC NERVE  PACE MAPPING OF PHRENIC NERVE			

Standard statistics (e.g., mean, standard deviation) will be used to summarize each variable. Data from index cryoablations and repeat cryoablations will be reported separately.

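### SAP 7.28 computes total fluoroscopy time from first ablation catheter insertion, so any fluoroscopy used earlier in the procedure is left out of a metric defined as the whole-procedure total

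*SAP*

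**What the plan says.** Protocol 4.1.7 gives the definition: "Total fluoroscopy time is defined as total fluoroscopy time used during the procedure". Protocol 12.7 and SAP 7.28 repeat it.

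Under that definition SAP 7.28 shows two CRF fields. The first is "What was the fluoroscopy timer at time of first ablation catheter insertion" (FFABLTM). The second is "What was the fluoroscopy timer at the end of procedure" (FPRENTM). The Analysis Methods of the same section name total fluoroscopy time among five time metrics that "are calculated as the difference between a single start time and a single end time".

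On where the procedure begins, Protocol 4.1.7 and SAP 7.28 both state: "Total procedure time is defined as time from first venous access to time of last catheter removal". The overview in Protocol 8.4.1 starts with sedation and venous access and continues: "Deploy diagnostic catheters and perform transseptal puncture". A baseline voltage map of the left atrium follows, then: "Perform baseline mapping of the pulmonary veins to assess for pulmonary vein potentials using a circular mapping catheter". Only after that mapping is it decided whether pulmonary vein isolation, and with it the first ablation catheter, is needed.

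**The concern.** The definition covers the whole procedure, but the calculation starts its clock part-way through. An analyst who follows the SAP exactly would report a number under a name and definition that it does not meet.

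The error can run in only one direction, towards apparently shorter exposure. That matters for interpretation because the study has no comparator arm (Protocol 5.2). A reader can judge the figure only against fluoroscopy times from elsewhere, and a window that starts late will look short beside a whole-procedure figure. Protocol 9.2 lists less fluoroscopy as a possible benefit, Protocol 9.3 lists more fluoroscopy as a possible risk, and Protocol 3.2 says the data are input to a future pivotal study.

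There is also a consequence inside the SAP. Isolation is not required when prior successful isolation is confirmed at the start of the procedure (Protocol synopsis, Study Design), and Protocol Table 2 does not make the balloon catheter mandatory. In such a subject ArcticLine may be the first ablation catheter. The total would then differ from fluoroscopy time during ArcticLine use only by fluoroscopy after ArcticLine is removed, although the two are listed as separate metrics.

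**Working it through.** The documents state no figure for this metric, so there is none to reproduce. The check compares the definition with the calculation rule.

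**Inputs**

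- S: timer reading at procedure start. It does not appear in the CRF excerpts in the SAP.
- FFABLTM: timer reading at first ablation catheter insertion (SAP 7.28).
- FPRENTM: timer reading at end of procedure (SAP 7.28).

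**Formulas**

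- Value meeting the definition: FPRENTM − S.
- Value under the SAP rule: FPRENTM − FFABLTM.
- Shortfall: (FPRENTM − S) − (FPRENTM − FFABLTM) = FFABLTM − S.

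**Bound**

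If the timer is not reset during the procedure, 0 ≤ S ≤ FFABLTM. The shortfall in each subject then lies between 0 and FFABLTM, and the true total lies between FPRENTM − FFABLTM and FPRENTM. The SAP value is exact only if no fluoroscopy is used before the first ablation catheter is inserted. If the timer were zeroed at that insertion, the bound would no longer apply, but the earlier fluoroscopy would still be missing.

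**Illustration (all readings assumed, in minutes)**

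| FPRENTM | FFABLTM | S | Defined total | SAP value | SAP error |
|---|---|---|---|---|---|
| 30 | 0 | 0 | 30 | 30 | 0% |
| 30 | 5 | 0 | 30 | 25 | 5/30 = 16.7% too low |
| 30 | 10 | 0 | 30 | 20 | 10/30 = 33.3% too low |
| 30 | 5 | 5 | 25 | 25 | 0% |

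With S = 0, letting FPRENTM run from 20 to 45 and FFABLTM from 0 to 10 gives an understatement from 0% to 50% (10/20).

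The last row shows why the end reading alone is not a safe substitute. If the timer already stood at 5 when the procedure began, FPRENTM by itself gives 30 against a true 25, which is 5/25 = 20% too high. The error of FPRENTM alone is +S, so the right correction depends on knowing S.

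**What is not affected**

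Fluoroscopy time during ArcticLine use has its own pair of timer fields, and fluoroscopy dose is not computed from these readings.

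**The case against.** The strongest reply is that this carries little weight. Objective 6 is summarised by means and standard deviations, no hypothesis test or decision rule uses it, and the primary endpoint does not depend on it. The SAP prints both field names beside the metric, so anyone reading the SAP can see the window. No passage plans an external comparison. What may be lost precedes any ablation catheter, and so precedes any use of ArcticLine. The documents contain no fluoroscopy minutes, so every percentage above comes from assumed inputs. All of this stands, and it limits the importance of the point without removing the mismatch.

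A second reply is that neither document fixes a clock start for the word procedure in the fluoroscopy definition. The sentence in Protocol 12.7, "A cryoablation procedure is considered to have occurred once the skin is punctured", is a rule for including subjects, and SAP 7.28 does not carry it forward. That is fair, and the argument does not need that sentence. Total procedure time starts at first venous access, and Protocol 8.4.1 lists the earlier steps as part of the procedure. No passage starts the procedure at insertion of the first ablation catheter.

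A third reply is that the SAP shows only excerpts of the CRF, so a start reading may exist elsewhere. That is possible and would make the correction easier. It would not change the rule as written, which uses the two fields shown.

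**Conclusion.** The concern holds. The SAP's rule gives a value that either matches the shared definition of total fluoroscopy time or falls below it, and nothing else in either document corrects it.

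Only the direction is established. The shortfall per subject is FFABLTM − S, between zero and FFABLTM provided the timer is not reset during the procedure. Its size cannot be derived from the documents and may be zero. The reading that the procedure includes the steps before the first ablation catheter rests on the venous-access start of total procedure time and on the order of steps in Protocol 8.4.1. The effect is confined to one descriptive ancillary metric. It should be corrected because the number would not meet its own definition and the remedy costs almost nothing.

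**What to change.** Choose one of two options and apply it to all subjects:

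1. **Correct the formula.** If the records show for every subject that the timer was zeroed at procedure start, or give a start reading, report FPRENTM minus that start reading as total fluoroscopy time.
2. **Correct the label.** Otherwise keep FPRENTM − FFABLTM and call it *fluoroscopy time from first ablation catheter insertion to end of procedure*. A footnote with the mean FFABLTM would show the most that can be missing on average, if the timer was not reset.

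Do not mix the two in one mean, and do not substitute FPRENTM alone without confirming the start reading.

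The first option costs a check of the procedure records of the 15 treated subjects. SAP 7.2.2 says all procedures are complete, so it is open only if those records already hold the start reading. The reported time may rise. The second option needs a table label and an optional footnote, with no new data.

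A side note for the same table: left atrial dwell time is defined to removal of the last sheath or catheter from the left atrium, but the SAP ends it at last sheath removal, a field that names no chamber. Dwell could be overstated if the left atrium is vacated before later right atrial work. Protocol 8.4.1 calls for a left atrial map after the waiting period, so this is possible but not shown. Labelling the metric *transseptal puncture to last sheath removal* would settle it at the cost of a second label.
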